5.10. Statistical Analysis

5.10.1. Subject Disposition

The number of patients included in the safety and efficacy populations will be tabulated. In addition, the disposition of patients who completed the study and who discontinued from the study will be presented. The reason for discontinuation from the study will be presented in a listing in Section 4.1.1.

5.10.2. Inclusion Criteria

A list of and exanet-treated patients not meeting one or more inclusion criteria will be presented.

5.10.3. Exclusion Criteria

A list of and exanet-treated patients meeting one or more exclusion criteria will be presented.

5.10.4. Protocol Deviations

Protocol deviations will be listed. Specific protocol deviations include the following:

- Those who entered the study even though they did not satisfy the entry criteria.
- Those who developed withdrawal criteria during the study but were not withdrawn.
- Those who received the wrong treatment or incorrect dose.
- Those who received an excluded concomitant treatment.

Details around protocol deviations specific to the primary efficacy endpoint are as follows:

Per the protocol, the percent change from baseline in anti-FXa activity to the nadir will be defined by a specific evaluation period as the period starting 3 minutes after the start of the andexanet bolus and ending 5 minutes after the end of the andexanet infusion. Acceptable windows around these times are defined in the Protocol (Appendix A, Schedule of Activities).

Samples drawn outside these windows may be considered significant protocol deviations, especially if they impact the integrity of the data. The protocol deviations may also be presented in a listing.

5.11. Treatment Compliance

Patient compliance with the andexanet treatment will not be evaluated as the treatment is performed in the hospital by a trained professional. The total dose of andexanet administered to each subject and the time from last dose of FXa Inhibitor to the start of andexanet for bolus will be summarized. In addition, any treatment modification and the reason for modification will be tabulated.

5.11.1. Demographic and Baseline Characteristics

Baseline and demographic characteristics such as such as age (years), weight (kg), height (cm), body mass index (BMI in kg/m²), ethnicity, race, sex, GCS, mRS, NIHSS, ICH score, Factor Xa Inhibitor, baseline hematology, chemistry, vital signs, medical history, mechanism of injury (spontaneous or traumatic), and ICH imaging characteristics (e.g., volume, thickness, midline shift, intraventricular involvement, supratentorial vs. infratentorial location) will be summarized

for both the safety and efficacy populations. Description of variable to be summarized are presented in Section 4.2.

For continuous variables, number of observations, mean, median, standard deviation, and minimum and maximum values will be presented. For categorical variables, counts, percentages will be tabulated for each category.

All available data will be included in the analysis. Missing values will not be imputed.

5.12. Concomitant Therapy

All medication used following informed consent through End of Study (Day 30) will be documented. Prior medications that are ongoing at the time of study enrollment are also recorded. All concomitant medications will be listed.

5.13. Efficacy Analysis

All efficacy analyses will be performed separately for each FXa inhibitor (i.e., apixaban, rivaroxaban, edoxaban and enoxaparin). In certain cases, a pooled analysis will be provided as well, and is indicated below where appropriate.

5.13.1. Primary Efficacy Analysis

Two primary endpoints will be evaluated:

- The percent change from baseline in anti-fXa activity to the on treatment nadir (i.e., minimum value between EOB and EOI).
- The achievement of hemostatic efficacy of stopping an ongoing major bleed at 12 hours from the end of the andexanet infusion, rated by the independent EAC as excellent or good.

The first objective is to demonstrate the decrease in anti-fXa activity following and examet treatment. Analysis will include all patients in the efficacy population. The following hypothesis will be evaluated:

Ho:
$$\mu = 0$$

H₁:
$$\mu \neq 0$$

The percent change in anti-fXa activity from baseline (last measurement before administration of andexanet) to post administration (the lowest level measured between the start of andexanet administration and 10 minutes after the end of the andexanet administration) will be calculated for each patient as %change = $100 \times (post - baseline)$ / baseline rounded to 1 decimal place. Percent change from baseline in anti-fXa activity will be evaluated using a distribution free two-

sided 95% CIs for the median. Because the data are expected to be non-normal, the distribution free confidence interval will be the primary for decision making. If the CI for the median excludes 0, the first primary objective will be considered to have been met. The CI will be calculated using distribution free methods using PROC UNIVARIATE in SAS as shown below.

```
proc univariate ciquantdf (alpha=.05);
var val;
ods output Quantiles=results;
run;
```

The second primary objective is to evaluate the hemostatic efficacy following and exanet treatment. Analysis will be performed including all patients in the efficacy population with valid EAC hemostatic efficacy adjudication (excluding events adjudicated as non-evaluable due to administrative reason). In addition, a sensitivity analysis will be conducted with the patients adjudicated as non-evaluable due to administrative reason rated as poor hemostatic efficacy.

The following hypothesis will be evaluated:

```
H_0: \pi = 0.50
```

 H_1 : $\pi \neq 0.50$

The proportion of patients in the Efficacy Analysis Population who are adjudicated to have effective hemostasis (excellent or good) by the independent EAC will be summarized. An exact 95% CI will be reported. The study will be considered to have met its second primary efficacy objective if the proportion of patients with excellent or good hemostasis (as adjudicated by the independent Endpoint Adjudication Committee [EAC]) is statistically significantly higher than 50% (p < 0.05). This test will be performed by calculating the exact binomial confidence interval and checking that it only contains points above 0.5. In addition to the confidence interval the one sided (right) p-value from the exact binomial test that the lower bound of the confidence interval will be higher than 50% will be presented. In SAS this will use the exact binomial option in PROC FREQ as shown below.

```
proc freq;
tables val binomial (p=.50) noprint;
exact binomial;
output out=results binomial exact;
run;
```

To maintain the type I error rate, the decision on the second primary objective will only be made if the first primary objective is met. This results in a fixed sequence multiple comparisons procedure.

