11.5. Efficacy Endpoints and Analyses

11.5.1. Definitions

For anti-fXa activity level-related efficacy endpoints, the baseline measurement will be the last value obtained prior to the start of the andexanet bolus. The evaluation period for anti-fXa activity covers the period of time from 5 minutes following the end of the andexanet bolus to 10 minutes after the end of the andexanet infusion. Hemostatic efficacy will be assessed from baseline through the 12 hour time point after the end of the andexanet infusion. As with anti-fXa activity, baseline is defined as the last assessment prior to the start of the andexanet bolus. Prior to assessment of hemostatic efficacy, the EAC will determine whether the patient meets bleeding entry criteria and whether the hemostatic efficacy is evaluable (i.e., if sufficient clinical data, such as hemoglobin and/or imaging results, are available to assess efficacy). The EAC will categorize the hemostatic response as excellent, good, poor/none, or non-evaluable based on the pre-specified definitions in Appendix B and Section 11.1. Re-bleeding episodes will also be evaluated by the EAC according to the following definition: bleeding (whether from the same anatomical site or from a different anatomic site) in patients within 24 hours of initial and examet treatment and after achieving initial good/excellent hemostasis. If a patient is re-dosed with and examet due to re-bleeding up through the 12 hour time point, the patient will be considered to have poor/none hemostatic efficacy.

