3.2. Sample Size

The sample size, as conceived in the original protocol, was based on the second primary efficacy variable. A sample size of 162 efficacy evaluable patients would provide 80% power for a two-sided 95% CI that is completely above 50% for the second primary efficacy variable of effective hemostasis, demonstrating a response rate above 50% for that variable. This is based on an anticipated response rate of 61%.

Also, it was estimated that ~30% of the safety population will have anti-fXa activity < 75 ng/mL (0.25 IU/mL for patients receiving enoxaparin) and therefore will not be included in the primary analysis. Additionally, it is estimated that up to 5% of patients will be non-evaluable for reasons unrelated to andexanet. Given these factors, the original sample size of the study was set to 250 patients. With the implementation of Protocol Amendment 4 (per a request from the FDA to enrich the enrolled population with ICH patients), enrollment was to continue until at least 110 evaluable ICH patients were enrolled to more comprehensively capture clinical outcomes in this high risk patient population. Therefore, to accommodate this request, the sample size was increased to a total enrollment of 350 patients.

With the implementation of Protocol Amendment 6, the final sample size was adjusted based on changes in enrollment strategy for various bleed types and FXa inhibitors, a need to meet regulatory requirements for sufficient numbers of patients for each FXa inhibitor and/or geographic region, or new information from registries, observational studies, clinical trials, and/or other sources. To accommodate a potential increase in sample size based on these factors, the overall enrollment was increased to 500 patients.

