4.3. Primary Efficacy Endpoints

The two co-primary efficacy endpoints are the decrease in anti-fXa activity following and examet treatment and the achievement of hemostatic efficacy. Anti-fXa activity will be evaluated at baseline, EOB, and at EOI, 4, 8, and 12 hours post-treatment. Anti-fXa activity will be expressed as ng/mL for apixaban, rivaroxaban, and edoxaban, and in IU/mL for enoxaparin.

The anti-fXa activity will be evaluated for the co-primary endpoint using percent change from baseline to on-treatment nadir.

The median percent change and 95% confidence intervals will be calculated separately for each FXA inhibitor.

The following variables will be calculated:

- On treatment Nadir: The on treatment nadir is the minimum value observed during treatment administration (i.e., minimum of EOB and EOI).
- Change from Baseline to On treatment Nadir: Change from baseline to On treatment Nadir is the reduction in anti-fXa activity from baseline to the minimum value during treatment administration (i.e., minimum value of EOB and EOI).
- Percent Change from Baseline to On treatment Nadir: The percent change from baseline
 to On treatment Nadir is the ratio between the Change from Baseline to On treatment
 Nadir, and the baseline, multiplied by 100.
- Percent Change from Baseline: The percent change from baseline is the ratio between the maximum change from baseline and the baseline, multiplied by 100.
- Percent Change from Baseline to EOI: The percent change from baseline to the EOI is the ratio between the Change from baseline to the EOI and the baseline, multiplied by 100.
- 12 hour Nadir: The 12 hour nadir is the minimum value observed post start of treatment evaluations (i.e., EOB to 12 hours post start of andexanet treatment).
- Area Under the Curve (AUC) for anti-fXa activity at each time point up to the 4 hours post end of infusion. The AUC will be calculated using trapezoid rule as follows:
 - Trapezoidal area calculation = ½ * (PCAFXa(x2) + PCAFXa(x1)) * (Time(x2) Time(x1)), where PCAFXa = Anti-fXa; X1 is first or earlier time point and X2 is second time point.

Hemostatic efficacy will be determined by the blinded EAC as excellent, good, poor/none, not evaluable due to administrative reasons, or not evaluable due to clinical issue based as described

in the study protocol and Endpoint Adjudication Charter. Hemostatic efficacy will be presented as follows:

- Excellent
- Good
- Poor/None
- · Not Evaluable

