5.0 STATISTICAL METHODS

5.1. General Considerations

All hypothesis tests will be 2-sided and reported at the 0.05 significance level. All CIs will be 2-sided and reported at the 95% confidence level unless stated otherwise. P-values will be rounded to 3 decimal places. P-values less than 0.001 will be presented at p < 0.001.

For continuous variables, the number of non-missing observations, mean, median, quartiles, standard deviation, minimum, maximum, and 95% confidence interval (CI) will be presented unless stated otherwise. Means, medians, quartiles, and 95% CI will be displayed to 1 more decimal place than the raw data and the standard deviation will be displayed to 2 more decimal places. The minimum and maximum will be displayed to the same number of decimal places as reported in the raw data. For categorical variables, the number of observations, the number of events, and percentages of events with the 95% CI will be reported. Descriptive summaries will be presented for the efficacy population as well as for the individual subgroup analyses.

It is anticipated that all statistical analyses will be performed using SAS Version 9.4 (SAS Institute, Inc., Cary NC) or higher. Additional software may be used for the production of graphics and for statistical methodology not provided by SAS. All summaries and analyses documented in this Statistical Analysis Plan (SAP) will be presented in the final integrated CSR. The CSR may also contain additional tables or statistical tests as warranted by the data obtained. The justification for any such additional analyses will be fully documented in the CSR.

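### The first primary test sets the lower of two post-dose samples against one baseline sample, so a zero median is the wrong null and the gate does not hold its stated 5% level

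*SAP*

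**What the plan says.** SAP 5.13.1 names the first primary endpoint as "The percent change from baseline in anti-fXa activity to the on treatment nadir (i.e., minimum value between EOB and EOI". SAP 4.3 defines the nadir in the same way: "The on treatment nadir is the minimum value observed during treatment administration (i.e., minimum of EOB and EOI". There is one baseline value per patient; Protocol 11.5.1 says "the baseline measurement will be the last value obtained prior to the start of the andexanet bolus".

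The null hypothesis in SAP 5.13.1 is zero change. A distribution-free two-sided 95% CI for the median decides the outcome: "If the CI for the median excludes 0, the first primary objective will be considered to have been met". SAP 5.1 sets the level: "All hypothesis tests will be 2-sided and reported at the 0.05 significance level". The result is also a gate. SAP 5.13.1 says "To maintain the type I error rate, the decision on the second primary objective will only be made" if the first objective has been met.

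The plan makes no correction for taking a minimum. Percent change to EOI is listed in SAP 4.3 as a derived variable, but no single-time-point comparison decides the objective. Under SAP 5.5.1, if one post-dose sample is missing the other is used, and if both are missing the change is set to zero.

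**The concern.** The minimum of two noisy measurements tends to lie below a single measurement of the same quantity. If anti-fXa activity did not change and the three samples differed only by assay and within-patient variation, most patients would still show a negative change to nadir. A rule that treats a median below zero as evidence of a decrease would then succeed by construction.

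At stake is the error rate that the SAP claims for the biomarker objective, and the purpose of placing that objective first in the sequence. The issue is separate from how the nadir window is worded and from whether a real decrease is caused by andexanet. It would remain with a consistent window and with no drug clearance.

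**Working it through.** **Inputs.** From the documents: two-sided 0.05 (SAP 5.1); minimum of EOB and EOI against one baseline (SAP 4.3, 5.13.1; Protocol 11.5.1); n = 162 (SAP 3.2); healthy-subject changes of -93.9% (SD 1.7) on andexanet and -20.7% (SD 8.6) on placebo (Protocol 11.6). Not given, so assumed: the correlation ρ between EOB and EOI deviations from the patient's true level, and the within-patient CV.

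**The plan's own figures.** SAP 3.2 says "A sample size of 162 efficacy evaluable patients would provide 80% power" for the hemostasis endpoint, and "This is based on an anticipated response rate of 61"%. The smallest k with P(Bin(162, 0.5) ≥ k) ≤ 0.025 is 94. P(Bin(162, 0.5) ≥ 94) = 2.46% and P(Bin(162, 0.61) ≥ 94) = 80.5%, so the stated 80% reproduces. The stated power above 99% for anti-fXa activity also reproduces: 93.9 / (1.7/√162) ≈ 703 standard errors.

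**The decision rule as a count.** At n = 162 the distribution-free CI for the median runs from the 69th to the 94th ordered value. It lies wholly below 0 when at least 94 of the 162 changes are negative.

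- One pre-named post-dose sample, no true change: P(negative) = 1/2. The CI lies below 0 in 2.46% of trials and excludes 0 on either side in 4.92%. The stated level holds.
- Minimum of two, no true change, independent deviations: baseline is the lowest of three exchangeable values with probability 1/3, so P(negative) = 2/3. P(Bin(162, 2/3) ≥ 94) = 99.1%. A simulation of the full procedure (20,000 trials) gave 98.9%.

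The 2/3 does not depend on the size of the error or on the spread between patients.

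**Correlated EOB and EOI deviations.** With normal deviations of equal variance, P(negative) = 3/4 − arcsin((1+ρ)/2)/(2π).

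| ρ | P(negative) | CI below 0 at n = 162 |
|---|---|---|
| 0 | 0.667 | 99% |
| 0.3 | 0.637 | 94% |
| 0.5 | 0.615 | 84% |
| 0.9 | 0.551 | 25% |

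**Other sample sizes (ρ = 0).** The rate is 43% at n = 30, 66% at 60, 90% at 100, and above 99.9% at 310. SAP 5.13 runs efficacy analyses by inhibitor, so the smaller sizes matter. The 310 is an assumption: 477 × (1 − 0.35), applying the planned 30% and 5% losses to the 477 patients in SAP 1.0.

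**Missing samples (n = 162, ρ = 0).** If a fraction f of patients has only one post-dose sample, P(negative) = (2/3)(1−f) + f/2. At f = 0.10 the rate is 97%, and at f = 0.20 it is 93%. If both samples are missing and set to zero in 5% or 10% of patients, it is 93% or 72%.

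**Size of the shift in the reported median.** With no drug effect, taking the minimum moves the median by about -2.7, -5.4 and -10.4 points for CVs of 5%, 10% and 20%. With a true change of -93.9%, post-dose values are 6.1% of baseline, so the shift is scaled by 0.061: -2.7 × 0.061 ≈ -0.2, -5.4 × 0.061 ≈ -0.3, and -10.4 × 0.061 ≈ -0.6 points.

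**The case against.** The best defence is that the interval is not miscalibrated. It covers the median of the change to nadir about 95% of the time, and SAP 5.13.1 states its null for that variable. This is correct. A reader might infer that the CI method is faulty, and it is not. What remains is that the objective is to demonstrate a decrease in anti-fXa activity, and a zero median change to nadir does not correspond to no decrease.

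A reader might also infer that hemostasis can be claimed falsely in 99% of trials. The documents do not support that. Hemostasis has its own exact CI against 50%, with a 2.46% upper tail at n = 162 even if the gate always opens.

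Nor do they support reading the expected reduction as an artefact. The multi-point shifts arise only with no drug effect; near -94% the shift is a fraction of a point.

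The 99% is also a ceiling. It needs pooled data, uncorrelated deviations and nearly complete sampling. Even so, 25% at ρ = 0.9 is about ten times the nominal lower tail.

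The strongest remaining objection is that zero is a poor reference even for a single sample. Placebo subjects fell by 20.7% (SD 8.6) within 5 minutes of bolus end. Under normality, about 99% of such subjects would be below zero (20.7/8.6 = 2.4 SDs), so an EOB comparison alone would exclude 0 without andexanet. This stands, and it limits what any correction to the minimum can achieve.

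**Conclusion.** The concern holds in a limited form. The first primary rule lacks the two-sided 5% level that the SAP assigns to it when the null is unchanged anti-fXa activity. At n = 162 the false-positive rate is up to 99%, falling to 84% at ρ = 0.5 and 25% at ρ = 0.9, and it is 43% at n = 30 with ρ = 0. These figures assume no true change and exchangeable samples (equal variances when ρ > 0), with both post-dose samples present; ρ is not in the documents. The first step of the sequence therefore gives little type I error protection for the biomarker claim.

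The practical weight is modest. If the effect in patients is near the healthy-subject figure, the met/not-met decision is the same and the reported median is overstated by about 0.2 to 0.6 points for assumed CVs of 5% to 20%.

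**What to change.** In SAP 5.13.1, keep the change to nadir as the reported endpoint and replace the decision sentence with: *The first primary objective is met only if the distribution-free 95% CIs for the median percent change from baseline at EOB and at EOI both lie entirely below 0.* Report both medians beside the nadir. This also states the direction, which a rule based only on excluding 0 leaves open.

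For missing data, use a patient with one post-dose sample only at the available time point, and keep the zero-change rule when both are missing. Record the change in SAP 5.17.2 as a departure from the rule in Protocol 11.5.6. Because SAP 1.0 refers to locked data, label any change made after lock as such.

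Each CI compares one post-dose sample with one baseline. Requiring both needs no alpha split: the lower-tail error is at most 2.46% at n = 162, and was 0.2% to 0.3% in simulation with independent deviations.

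The cost is SAP text and one more run of the same PROC UNIVARIATE step; both samples are already scheduled. The rule is slightly stricter and the single-time-point medians will be slightly less favourable. At the expected effect nearly every observed change is negative and only 94 of 162 are needed at each time point, so little power should be lost. The documents give no separate EOI figure to confirm this.

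The change removes only the error from selecting a minimum. It does not attribute the decrease to andexanet, given the placebo fall, and it does not remove regression to the mean from admitting patients to the Efficacy Population on the same baseline value. The report should state both limits.

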11.1. General Considerations

It is anticipated that statistical summaries will be performed using SAS Version 9.2 (SAS Institute, Inc., Cary, NC, USA) or higher. Additional software may be used for the production of graphics and for statistical methodology not available in SAS.

All hypothesis tests will be two-sided and reported at the 0.05 significance level. All CIs will be two-sided and reported at the 95% confidence level.

As part of their role, the EAC is tasked to determine whether there is sufficient information available to make a valid assessment. If the case is adjudicated by the Committee as non-assessable, it will be further classified as non-evaluable due to administrative reasons (e.g., follow-up scan not available) or non-evaluable due to clinical reasons (e.g., patient died). The criteria for which a subject may be rendered non-evaluable for hemostatic efficacy will be further specified in the Adjudication Charter.

Both primary objectives will be assessed using patients who have a baseline anti-fXa level at or above the evaluability threshold (75 ng/mL for apixaban and rivaroxaban, 40 ng/mL for edoxaban, 0.25 IU/mL for enoxaparin). A supportive analysis will examine the same endpoints in patients who have a baseline anti-fXa level of less than the threshold value. Another supportive analysis will assess all patients, with stratification by baseline anti-fXa level of at least or less than the threshold value.

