11.5.6. Statistical Methodology for Endpoint Analyses

The first primary efficacy endpoint, i.e., percent change in anti-fXa activity from baseline (last measurement before administration of andexanet) to nadir (the lowest level measured between 5 minutes prior to the start of andexanet administration and 10 minutes after the end of the andexanet administration) will be calculated for each patient as change = 100 %×(post-baseline)/baseline. Percent change from baseline in anti-fXa activity will be assessed with two-sided 95% CIs. A nonparametric CI for the median will be reported. If the nonparametric CI for the median excludes 0, the first primary objective will be considered to have been met. For the first primary endpoint, patients who do not have at least one anti-fXa activity level within the evaluation period for non-administrative reasons will have percent decrease imputed as 0.0% (i.e., using the baseline value as the nadir value).

The second primary efficacy endpoint, proportion of efficacy evaluable patients who are adjudicated to have effective hemostasis (excellent or good) by the independent EAC will be summarized as a point estimate with an asymptotic 95% confidence interval.

To maintain the type I error rate, the statistical evaluation of the primary endpoints, including the analysis of hemostatic efficacy in specific study populations against specific comparators, will be ordered in a fixed sequence multiple comparisons (hierarchical) procedure.

The secondary endpoint will be assessed by plotting the Receiver Operating Characteristics (ROC) curve and calculating the Area Under the Curve (AUC). Patients will be classified as success or failure based on achievement of hemostatic efficacy. For each potential cut point of a percent change in anti-fXa activity, the sensitivity and specificity of that cut point to distinguish achievement of hemostatic efficacy will be calculated. The ROC plots sensitivity by 1 - specificity. An AUC of 0.5 or lower indicates that the percent change in anti-fXa activity does not predict achievement of hemostatic efficacy. An AUC of 0.7 or higher is indicative of a relationship that is more useful in predicting hemostatic efficacy [27]. The Minimum Clinically Important Difference (MCID) of percent decrease in anti-fXa activity will be derived as the value that simultaneously maximizes sensitivity and specificity.

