5.17.2. Changes to the Analysis Plan

This analysis plan is an update to version 3.0 (09 August 2019). The main changes to version 3.0 of the Statistical Analysis Plan are:

- 1) Remove stratification of Generation 1 and 2 from all analyses
- Include an extra definition and summary of Thrombotic Events using a broader list of preferred terms, per FDA request
- 3) Reclassify Urinary Bleeds from the "GI" category to the "Other" category
- 4) Pre-specify an analysis of the
 - a. correlation between reversal of anti-fXa activity with effective hemostasis, and
 - b. correlation between reversal of anti-fXa activity with mortality

Previous Changes to SAP

The previous analysis plan was an update to versions 1.0 (30 October 2018) and 2.0 (21 November 2018). The main purpose of changes to the versions 1.0 and 2.0 of the Statistical Analysis Plan was to accommodate additional patients treated with edoxaban and patients in Japan, and to align the SAP with the last version of the protocol (i.e., amendment 5 and 6).

The main change to the SAP (as in the protocol) regards the definition of efficacy evaluable patient population to include requirement of a minimum anti-fXa activity level for edoxaban as follows:

The Efficacy Population will include all patients in the Safety Population who meet all of the following criteria:

- · Are determined by the EAC to meet the clinical bleeding inclusion criteria.
- Have a baseline anti-fXa level
- Baseline anti-fXa level of at least 75 ng/mL for apixaban and rivaroxaban, 40 ng/mL for edoxaban, or 0.25 IU/mL for patients receiving enoxaparin.

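### Does naming a one-sided p-value beside p < 0.05, and an exact rather than asymptotic interval, leave the second primary test unclear?

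*SAP*

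**What the plan says.** SAP 5.13.1 sets a null response rate of 0.50 against a two-sided alternative. The second primary objective is met if the proportion with excellent or good hemostasis "is statistically significantly higher than 50% (p < 0.05". The next sentence says how that test is done: compute the exact binomial confidence interval, "checking that it only contains points above 0.5". The p-value comes after that, as something to be presented: "In addition to the confidence interval the one sided (right) p-value from the exact binomial test". No cut-off is attached to it.

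The general rules are two-sided in both documents. SAP 5.1: "All hypothesis tests will be 2-sided and reported at the 0.05 significance level". Protocol 11.1: "All hypothesis tests will be two-sided and reported at the 0.05 significance level". Both also fix two-sided 95% intervals. SAP 3.2 sizes the study at 162 evaluable patients for "80% power for a two-sided 95% CI that is completely above 50" percent, assuming a true rate of 61%.

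On the type of interval, Protocol 11.5.6 (and the synopsis in the same words) says the proportion "will be summarized as a point estimate with an asymptotic 95% confidence interval". SAP 5.13.1 reports an exact interval. The current list in SAP 5.17.2 opens with "The main changes to version 3.0 of the Statistical Analysis Plan are" and does not mention interval type.

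**The concern.** Two things look wrong on a first reading. First, a 0.05 threshold and a one-sided p-value stand in the same paragraph, and 0.05 is the only threshold printed there. Someone who puts them together would be testing at one-sided 5%, twice the upper-tail error of a two-sided 95% interval. The study report could then show a p-value under 0.05 next to an interval that includes 50%, and a reader might take the objective as met when it was not.

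Second, the protocol names one type of interval and the SAP another for the same primary endpoint. If the two gave different verdicts near the boundary, the choice would matter, and one would want it recorded as a change.

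**Working it through.** **Inputs.** Null rate 0.50 (SAP 5.13.1); true rate 0.61 and n = 162 (SAP 3.2, Protocol 11.6); two-sided 95% intervals (SAP 5.1, Protocol 11.1); 477 patients in the locked database (SAP 1.0); about 30% below the anti-fXa threshold and up to 5% otherwise non-evaluable (SAP 3.2).

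**Formulas.** With x responders out of n:
- Exact (Clopper-Pearson) lower limit: the 2.5% quantile of Beta(x, n − x + 1). It exceeds 0.5 exactly when P(X ≥ x | n, 0.5) < 0.025.
- Asymptotic (Wald) lower limit: p − 1.96 × √(p(1 − p)/n), with p = x/n.
- One-sided exact p-value: P(X ≥ x | n, 0.5). The two-sided value is twice this, because the binomial at 0.5 is symmetric.

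**Step 1: reproduce the plan's figure.** At n = 162 the smallest x with an exact lower limit above 0.5 is 94 (58.0%; limit 50.03%).
- Upper-tail error: P(X ≥ 94 | 162, 0.50) = 2.46%.
- Power: P(X ≥ 94 | 162, 0.61) = 80.5%, against the stated 80%.

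The first n reaching 80% power is 162 for the exact two-sided rule, 152 for the asymptotic interval and 130 for one-sided p < 0.05. The planned 162 therefore matches the rule the SAP says it will apply.

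**Step 2: when could the one-sided p-value mislead at n = 162?**

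| Responders | One-sided p | Two-sided p | Exact lower limit |
|---|---|---|---|
| 91 | 0.068 | 0.135 | 48.2% |
| 92 | 0.049 | 0.099 | 48.8% |
| 93 | 0.035 | 0.070 | 49.4% |
| 94 | 0.025 | 0.049 | 50.0% (50.03%) |

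Only 92 and 93 give a one-sided p below 0.05 with an interval that includes 50%. At a true rate of 61% the chance of landing on either is 7.6%. If 92 were wrongly used as the cut-off, the upper-tail error would be 4.93%.

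**Step 3: exact against asymptotic.** At n = 162 the asymptotic lower limit at 94 is 0.5802 − 1.96 × √(0.5802 × 0.4198/162) = 50.4%, and at 93 it is 49.8%. The cut-off is again 94. Over all 316 values of n from 162 to 477, the asymptotic cut-off is one responder lower at 188 values and never more than one lower. Its largest upper-tail error is 3.07% (n = 165). The exact rule stays at or below 2.5% throughout.

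**Step 4: a plausible larger n.** The documents give no evaluable count, so this is an assumption. Applying the planning exclusions in sequence gives 477 × 0.70 × 0.95 ≈ 317; adding them gives 477 × 0.65 ≈ 310.
- n = 310: both intervals need 173.
- n = 317: exact needs 177, asymptotic 176. At 176 the lower limits are 49.86% and 50.05%, and the two-sided p is 0.056.

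At a true rate of 61% and n = 317 about 193 responders are expected (0.61 × 317). The chance of exactly 176 is 0.6%. The chance of 174 to 176, where the one-sided p is below 0.05 but the exact interval includes 50%, is 1.5%.

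**The case for a change.** The strongest case for a change is that this is a primary success statement, and the only printed threshold does not fit the only named p-value. A one-sided p-value would have to be compared with 0.025 to agree with the interval, and the SAP does not say so. It also sits oddly with the two-sided hypothesis in the same section and with the general rule. Further, replacing a named interval method is more than added detail, and at some sample sizes it can turn a verdict on one patient.

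The wording mismatch stands. The consequence does not. The sentence after the threshold defines the test as the interval check, so 0.05 belongs to the two-sided 95% interval, and the p-value is an addition to it. A misreading requires applying 0.05 to a supplementary figure while ignoring the stated rule and the interval printed beside it.

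On interval type, the protocol says only that the endpoint is summarised with an asymptotic interval. Where it states what must be shown (synopsis and 11.6), it names no type. Sections 11.0 and 11.5.6 leave further detail to the SAP. The SAP's choice is the more conservative of the two and matches the sample size.

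No omission can be read from SAP 5.17.2. Its current list covers the main differences from SAP version 3.0, and that version is not available to show whether the exact interval was already there.

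**Conclusion.** No change to the plan is needed. Followed as written, SAP 5.13.1 gives one sound decision: success if the two-sided exact 95% interval lies wholly above 50%. That holds the upper-tail error at or below 2.5% and reproduces n = 162 with 80% power (80.5%). There is no inflated type I error and no arithmetic fault.

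What remains is a presentational slip that an analyst would settle when labelling the table, and a difference in wording between protocol and SAP worth at most one responder. Neither touches the sample size, the power or the decision rule. The results at n = 162 rest only on figures in the documents. The n = 310 and 317 illustrations assume that the planning exclusion rates apply to the 477 patients, and the chances of a borderline result assume the planned 61% rate.
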